5. STUDY'S AIM AND OBJECTIVES

AIM: To obtain pilot data to test the hypothesis that aeroallergen sensitisation (confirmed by a wheal formation with a diameter ≥ 3 mm after a skin prick test is performed), FeNO (offline method) ≥ 10 ppb and a peripheral blood eosinophil count $\geq 300/\mu\text{l}$, alone or in combination, can predict future wheezing exacerbations in preschool children as well as response to treatment with inhaled corticosteroids, as a preliminary to a large, randomised controlled trial. Also, that these tests are acceptable to families.

OBJECTIVES:

- To recruit 100 preschool children with a history of wheeze, aged one to five years old, and determine atopic status, peripheral blood eosinophil count (point of care test) and FeNO (offline method).
- To evaluate the feasibility and acceptability of these tests
- To categorize the children according to the biomarkers tested and assess whether any or all, alone or in combination, predict future wheezing exacerbations as well as determine the clinical outcome over one year
- To obtain parents' and doctors' insights into whether the biomarkers mentioned above could be used in a future intervention study.

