In the event that a child has had their ICS treatment discontinued, we will record whether this was because the treatment was ineffective (treatment failure) or if the child was so well that the family or GP did not wish to continue (treatment success or spontaneous improvement). If an additional medication is prescribed, or the child is referred to secondary care, this will be considered as treatment failure. When the study ends, participants' parents/carers will be invited to a face-to-face focus group interview, or a one-to-one interviews, or remotely through Microsoft Teams, depending on their availability at the end of the study period. The focus group and one to one interviews will utilise a semi structured questionnaire, to provide qualitative feedback on the acceptability of the 3 biomarker tests. In addition, a separate focus group for doctors and nurses will be conducted to assess the feasibility of the 3 biomarker tests being used in clinical practice. They will be given all the information regarding the study as well as the study's patient information sheet. Those agreeing to take part, will sign a consent form. They will be attending either a face-to-face focus group interview, or a one-to-one interview, or remotely through Microsoft Teams, depending on their availability. A semi structured questionnaire will be utilised. Where possible a second independent researcher will sit in the focus groups discussion and interviews to ensure there is no bias. The conversations from the focus group and one to one interviews will be transcribed and coded into themes. We will utilise an external company for transcribing the conversations called 1st Class. <https://www.1stclass.uk.com/>

The focus group and one to one interviews will be audio recorded, transcribed and put into themes to conduct an inductive thematic analysis. 25% of the transcripts will be

double coded by an independent researcher, experienced in qualitative research to ensure that the correct themes have been used and to ensure that there is no bias. The focus group and one to one interviews will be used to assess the acceptability and feasibility of measuring biomarkers in primary care and using them to help determine management of preschool wheeze.

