In addition, we will ask them to fill in a very short electronic questionnaire after the study is finished, to check their perspective and acceptability on these biomarkers being used to guide children's therapy in the future (Appendix 5: Exit Questionnaire).

The whole duration of this study is expected to be 20-21 months, with 1-year follow-up for each patient included.

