7.3. WITHDRAWAL CRITERIA

Parents can withdraw their child at any time without having to justify their decision. Upon withdrawal, patients will continue in their usual clinical care. In addition, the investigator may withdraw a child participant from the study if it is considered necessary to protect their wellbeing or that of others. Child participants' data will be retained and included in the final study analysis, unless the parent/carer specifies otherwise. Reasons for withdrawal, where available, and timing of withdrawal will be collected and recorded. Attempts to replace child participants whose parents decided to withdraw, will be made in line with recruitment procedures outlined in section 4. If the child participant is withdrawn due to an adverse event, the research team will

arrange for follow-up visits or telephone calls to monitor the adverse event until it has resolved or stabilised.

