10. END OF STUDY

The end of the study will be when the last of the 100 participants completes his follow-up period of 12 months with his/her last study visit. The anticipated finishing date is December 2023.

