19.5. APPENDIX 5: EXIT QUESTIONNAIRE

Introduction: Thank you for participating in this study. We are really grateful for your willingness to help and volunteer for a study that aims to provide better wheezing treatment for our children in the future. Please take a moment to give us your feedback relating to the 3 biomarkers that were tested in this study as well as some comments on what you think the future definitive study should entail?

Question 1: How satisfied are you with this whole 1-year follow-up period study?

Very Dissatisfied	Dissatisfied	Neutral	Satisfied	Very Satisfied
				

Question 2: As a parent would you be interested in having the biomarker-based approach for your child in the future?

Yes	No	Maybe
		

Question 3: Did the study's 1-year follow up period help you change your mind on the 3 biomarkers (blood eosinophil count, FeNO and atopic sensitisation) being used in clinical settings for personalising treatment?

Not at all	Slightly	Moderately	Quite a lot
			

Question 4: Would you recommend this approach to other parents with children experiencing the same wheezing conditions?

Not at all	Maybe	Recommend	Highly recommend
			

Question 5: What else would you like to see in the future clinical trial? Would you change anything on the current process? What was good, what was not good?

Comment:

Survey's ending message: "Thank you for participating in our survey!"

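### Parents are asked about acceptability only at study end and nothing is asked at withdrawal, so any acceptability summary is open to attrition bias, probably upward

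*Combined protocol and SAP*

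**What the plan says.** Section 5 lists among the objectives "To evaluate the feasibility and acceptability of these tests", and its aim includes acceptability to families. Section 5.1 names acceptability as part of the benefit the study will generate, and Section 4.3 says it has to be determined before the large trial.

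Parents' views come from two sources:

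- **Exit questionnaire.** Section 6 (repeated in 7.1, and in substance in Section 2) says "we will ask them to fill in a very short electronic questionnaire after the study is finished, to check their perspective and acceptability"; the sentence goes on to refer to future use of the biomarkers in guiding therapy.
- **Focus groups and interviews.** Section 6 says "When the study ends, participants' parents/carers will be invited to a face-to-face focus group interview", with one-to-one or remote alternatives. Table 2 in Appendix 2 places the focus group at month 12.

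Section 10 defines the end point of the study: "The end of the study will be when the last of the 100 participants completes his follow-up period of 12 months". The monthly questionnaire in Appendix 4 has no item on the tests.

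Two of the five exit items in Appendix 5 refer to the year of follow-up: Question 1 ("How satisfied are you with this whole 1-year follow-up period study") and Question 3 ("Did the study's 1-year follow up period help you change your mind on the 3 biomarkers"). Questions 2, 4 and 5 do not depend on having completed it.

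On leaving the study, Section 7.3 says "Parents can withdraw their child at any time without having to justify their decision". It records the timing of withdrawal, and the reason if one is available. It keeps the child's data unless the parent objects, and it attempts to replace the child. It plans no acceptability question at that point. Section 11 gives no acceptability measure, denominator or rule for missing responses.

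**The concern.** The required tests are done at the first study visit, but opinion on them is sought about a year later, and only at a time when withdrawn families have no planned contact with the study. Read literally with Section 10, the gap for the earliest recruits could reach about 21 months (9 months of recruitment plus 12 of follow-up). Families who leave because of the skin prick, the finger prick or the burden of visits are the ones whose views bear most on acceptability. As planned, no step ensures that they are asked.

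At stake is how the result is read. Acceptability among families who stayed for a year could be taken as acceptability among all families who entered. The study exists to inform a larger randomised trial, and a favourable summary resting mainly on stayers would be a weaker guide than it appears. Once a family has left without being asked, its view may not be recoverable.

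**Working it through.** There is no stated figure to reproduce. Section 6.1 does not list acceptability as an outcome, and Section 11 gives no acceptability proportion, threshold or denominator. No withdrawal rate appears anywhere. The arithmetic below shows only how the bias behaves under assumed values.

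**Inputs**

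- From the documents: the target in Section 5, "To recruit 100 preschool children with a history of wheeze, aged one to five years old"; attempted replacement of withdrawn children (Section 7.3).
- Assumed: proportion withdrawn *w* = 10%, 20%, 25%; favourable rate among completers *c* = 90%; favourable rate among leavers *l* = 90%, 50%, 30%, 0%. Every completer is assumed to respond.

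**Formulas**

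- Rate over all enrolled families = (1 − *w*)*c* + *wl*
- Overstatement by the completer rate = *c* − [(1 − *w*)*c* + *wl*] = *w*(*c* − *l*)

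**Results with *c* = 90%: all-enrolled rate (overstatement in points)**

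| *w* | *l* = 90% | *l* = 50% | *l* = 30% | *l* = 0% |
|---|---|---|---|---|
| 10% | 90% (0) | 86% (4) | 84% (6) | 81% (9) |
| 20% | 90% (0) | 82% (8) | 78% (12) | 72% (18) |
| 25% | 90% (0) | 80% (10) | 75% (15) | 67.5% (22.5) |

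For example, *w* = 0.25 and *l* = 0.30 give 0.25 × (0.90 − 0.30) = 0.15.

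**Sign.** The bias is upward only if leavers are less favourable than completers. With *c* = 80% and *l* = 90%, the completer rate is too low by 1 point at *w* = 10% (0.10 × (0.80 − 0.90) = −0.01), 2 points at 20% and 3 points at 30%.

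**Replacement.** At 20% withdrawal, obtaining 100 completers takes 100/0.80 = 125 enrolled families. If 90 of the 100 completers are favourable, the completer rate is 90%. With no leaver counted as favourable, the rate over everyone enrolled is 90/125 = 72%, the same as the 20% entry in the last column. Replacement therefore leaves the completer rate unchanged. What it changes is the denominator needed to see the loss, which is 125 and not 100.

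**The case against.** The strongest reply is that the plan defines no acceptability figure that could be biased. Acceptability of the tests themselves is explored mainly through interviews and focus groups analysed thematically, which yield no percentage. The exit form asks mostly about future biomarker-guided care. Acceptability is also not a listed outcome. This stands to the extent that no particular number can be called wrong. It does not remove the risk, because the focus groups and interviews have the same end-of-study timing and any tabulation of the exit form would carry the same selection.

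A reader might infer that withdrawn families are excluded. The documents do not say so. The invitation is addressed to participants' parents in general, Section 7.3 retains withdrawn children's data, and the consent form, which might cover later contact, was not available for this review. What can be said is narrower: no planned step obtains their answer.

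A reader might also take the exit form as a whole to be written for completers. Only Questions 1 and 3 are; an early leaver could answer the other three as they stand.

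Finally, withdrawal may have little to do with the tests. Required testing is a single visit that normally takes no more than an hour, and the repeat is optional. Later exits could reflect the monthly forms or a child who is now well. In that case the bias could be near zero or even negative. Recorded reasons for withdrawal and uptake of the optional repeat test would give some indirect evidence. This is fair, and it is why the direction is called probable and not established.

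**Conclusion.** The point holds as a risk of attrition bias in any acceptability summary. It rests on three features of the text: parents are asked only at study end, nothing is asked at withdrawal beyond a reason if available, and no denominator is set. Upward bias is the more plausible direction, since needle tests and repeated visits are among the burdens that could lead a family to leave, but the documents do not establish it.

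With 90% of completers assumed favourable and 10–25% withdrawn, the overstatement is 0 points if leavers answer like completers and 4–15 points if 30–50% of them are favourable. At 20% withdrawn with no favourable leaver it is 18 points. These sizes depend wholly on the assumed rates.

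It would go too far to conclude that the acceptability result is inflated, because no such figure is defined and neither the withdrawal rate nor leavers' views are known. It would also be wrong to say that replacing leavers adds to the bias: it can hide the loss only if the number ever enrolled goes unreported. This is a modest, inexpensive improvement to a feasibility study and not a flaw that undermines it.

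**What to change.** **Section 7.3.** Add that, at withdrawal, the family is offered Questions 2, 4 and 5 of Appendix 5 through the existing electronic form, with an explicit right to decline. These items need no rewording; Questions 1 and 3 should be left out for this group.

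**Section 11.** State which answers to Questions 2 and 4 count as favourable (Question 5 is free text). Report the number of families ever enrolled, including those replaced. Give acceptability in three ways:

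1. completers only;
2. completers plus withdrawn families who responded;
3. all enrolled families, with non-responders counted as not favourable, as a lower bound.

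The cost is one extra trigger for a survey that already exists and short additions to two sections. The downside is small: some withdrawn families will not answer, so the lower bound is still needed.

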6.1. STUDY OUTCOME MEASURES

Primary outcome:

Acute attacks of wheeze defined as requiring an unscheduled health care visit

Secondary outcomes:

- Carer days off work
- Days the child unable to attend childcare facility
- Use of oral corticosteroids
- Use of inhaled β -2 agonist (rescue therapy)
- Assessment if children's respiratory or wheezing condition is under control by using the TRACK™ score questionnaire (Test for Respiratory and Asthma Control in Kids) (Appendix 3).

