DESIGN:	This is a pragmatic, observational study in children with pre-school wheeze. After recruitment and at the first study visit, biomarkers (allergic sensitisation, exhaled nitric oxide and peripheral blood eosinophil count) will be measured. The children will be followed for a year, with monthly electronic questionnaires and study visits every 3 months. All treatment and routine monitoring decisions will be at the discretion of the children's general practitioner (GP) or paediatrician (as per usual clinical practice), blinded to the study measurements. There will be a second optional biomarker measurement 3 months after the first one, in their second study visit. Parents/Carers of preschool children presenting either to primary care or to the Emergency Department (ED) or to secondary care (e.g., outpatients) as well as of those identified from primary care records and have been diagnosed by their GP or paediatrician with wheezing, will be identified by collaborating doctors and nurses who will ask the parents if they are willing to have their child participate in the study (the list of recruitment sites is given in Appendix 1 – Recruitment Plan). A patient information sheet will be given, containing all the information regarding the

[figure not shown]

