Follow-up: We will arrange for a short monthly electronic questionnaire to be sent by email to the parents/carers, in order to record on a monthly basis, the days their child was out of childcare, days the carer missed from work, unscheduled health care visits and use of rescue therapy or oral corticosteroids (including dosage) (Appendix 4: Monthly Questionnaire). In addition, we will record the children's TRACK™ score (Test for Respiratory and Asthma Control in Kids) (Appendix 3: TRACK™ score questionnaire) every 3 months, to assess wheeze control. The questionnaires will be made and sent through the Qualtrics® questionnaire platform (offered by Imperial College London). There will be review visits every 3 months, to evaluate their progression in person, but if not feasible, video calls will be arranged through Microsoft Teams. Correct use of spacers will be ensured after guiding parents on how to use them and will be done by their GP or paediatrician as well as from [name] who is a registered pharmacist in the UK.

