9. ASSESSMENT AND FOLLOW-UP

We will arrange for a short monthly electronic questionnaire to be sent by email to the parents/carers, in order to record on a monthly basis, the days their child was out of childcare, days the carer missed from work, unscheduled health care visits and use of rescue therapy or oral corticosteroids (including dosage) (Appendix 4: Monthly Questionnaire). In addition, we will record the children's TRACK™ score (Test for Respiratory and Asthma Control in Kids) (Appendix 3: TRACK™ score questionnaire) every 3 months, to assess wheeze control. There will be review visits every 3 months, to evaluate their progression in person, but if not feasible, video calls will be arranged through Microsoft Teams. In the case of any incidental findings, there will be thorough evaluation of potential benefits or harms before disclosing the information to the child's parent. As this is an observational study, no interventions can be done in the case of incidental findings and parents will be advised to discuss this with their child's GP or paediatrician.

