11. STATISTICS AND DATA ANALYSIS

The statistical analysis of the project will be done by [name] in collaboration with [name] (University of Edinburgh) and the Asthma UK Centre for Applied Research (AUKCAR), the funder of the study. Statistical analyses will use the GraphPad PRISM software package. A normality test will be performed to assess normal (Gaussian) distribution (e.g., the Shapiro-Wilk test. If there is normal distribution, then parametric tests will be used, otherwise non-parametric tests. Level of significance is set as a p value <0.05. The tests that are currently planned to be used are:

- **Chi-Squared test (x²-test)**

This test allows assessing if a variable is similar between two or more groups or to test if two or more variables are related/dependent

- **Fisher's Exact test**

This test is used when chi-squared values are <5, usually with a small sample size.

- **Student t-test or Mann-Whitney test**

These tests are used for comparison between two study groups. The first is for normally distributed quantitative variables and the second for non-normally distributed quantitative variables.

Data and all appropriate documentation will be stored for a minimum of 10 years after the completion of the study, including the follow-up period.

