19.4. APPENDIX 4: MONTHLY QUESTIONNAIRE

Introduction: Please take a moment to complete the following questionnaire relating to your child's wheezing condition. The questions will help us identify wheezing exacerbations and assess your child's quality of life.

Question 1: Did your child experience any wheezing symptoms during the last month?

Not at all	Once or twice	Once every week	2 or 3 times a week	4 or more times a week
				

Question 2: Was the child unable to go to childcare because of breathing problems?

Yes	No	N/A
		

If **yes**, please state how many days: _____ (Number)

Question 3: Did you have to take your child for an emergency appointment with your GP, urgent care or hospital because of wheezing?

Not at all	Once or twice	Once every week	2 or 3 times a week	4 or more times a week
				

Question 4: Was your child treated with inhaled or oral corticosteroids?

Yes	No
	

If **yes**, what was the dose, frequency and duration?

Dose:	Frequency:	Duration:
_____	_____	_____

Question 5: Was your child given β 2 agonists (blue inhaler, rescue therapy)?

Yes	No
	

If **yes**, what was the dose, frequency and duration?

Dose:	Frequency:	Duration:
_____	_____	_____

Question 6: Did you have to take days off work because your child had wheezing or breathing difficulties?

Yes	No
	

If **yes**, how many days did you take? Specify number: _____ (days)

Survey's ending message: "We thank you for your time spent taking this survey. Your response has been recorded."

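### The primary outcome is attacks of wheeze, but the monthly form records only banded, undated visits and no rule says when several visits are one attack, so the number of attacks cannot be determined

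*Combined protocol and SAP*

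**What the plan says.** The study summary (section 2) and section 6.1 give the same primary outcome: "Acute attacks of wheeze defined as requiring an unscheduled health care visit". Neither adds an episode length, a symptom-free gap or a treatment of repeat visits.

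The follow-up text describes what is collected. Section 9 has the monthly questionnaire record "the days their child was out of childcare, days the carer missed from work, unscheduled health care visits and use of rescue therapy" as well as oral corticosteroids. The matching item, Question 3 in Appendix 4, reads "Did you have to take your child for an emergency appointment with your GP, urgent care or hospital because of wheezing". Its answers are five frequency bands. The lowest non-zero band covers one or two occurrences, and the higher bands are weekly rates. There is no number field, no date and no separation by place of care. The form's introduction says "The questions will help us identify wheezing exacerbations and assess your child's quality of life", but no algorithm follows.

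On schedule, section 2 says "The children will be followed for a year, with monthly electronic questionnaires and study visits every 3 months". Section 11 lists chi-squared, Fisher's exact, t and Mann-Whitney tests and says "Level of significance is set as a p value <0.05". It does not say which test is for the primary outcome, or whether that outcome is a count of attacks or any versus none.

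**The concern.** The unit named in the outcome (attack) differs from the unit recorded (visit), and nothing converts one into the other. A wheezing child may be seen by the GP and then in hospital within a day or two. To count attacks, an analyst needs to know that these visits belong together. That takes a rule, plus dates to apply it to, and the plan specifies neither.

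Two uses of the data depend on this. Section 4.3 wants pilot data for the power calculation of the later randomised trial; if that trial counts attacks, it needs an attack rate and its variance. Section 5 wants to know whether the biomarkers predict exacerbations. If a visit count stands in for attacks, it mixes how often a child has attacks with how many contacts each attack generates.

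Replacing the bands with an exact number of visits would not be enough: a perfect visit count still needs a joining rule.

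**Working it through.** The plan gives no event rate, visits-per-attack figure or power calculation for this outcome, so there is no stated figure to reproduce. The target of 100 children (section 5) is a recruitment number.

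**1. What Question 3 returns.**

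| What happened | Attacks | What the forms show |
|---|---|---|
| One attack, one visit | 1 | Lowest non-zero band, one form |
| One attack, GP then hospital in the same month | 1 | Lowest non-zero band, one form |
| Two attacks in one month, one visit each | 2 | Lowest non-zero band, one form |
| One attack, visits on either side of a form boundary | 1 | Lowest non-zero band, two forms |
| Two attacks, one visit each, in adjacent months | 2 | Lowest non-zero band, two forms |

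The first three rows cannot be told apart. Nor can the last two.

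**2. Range for a year.** A child with k months in the lowest non-zero band has between k and 2k visits. For k = 4 that is 4 to 8 visits. At most, each visit is its own attack: 8. If the four months are consecutive, with one visit in each, and visits pair across the boundaries of months 1–2 and 3–4, there are 2 attacks. The same four answers are compatible with 2 to 8 attacks.

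**3. Boundary crossing.** Assume 30-day months and uniform timing. Two visits d days apart fall on different forms with probability d/30:

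- d = 1: 1/30 = 3.3%
- d = 3: 3/30 = 10%
- d = 7: 7/30 = 23.3%

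This applies only to attacks with a second visit. If a fraction q of attacks have one, the share of attacks appearing on two forms is q × d/30: from 0.1 × 1/30 = 0.3% to 0.4 × 7/30 = 9.3% over q = 0.1 to 0.4. These values of q are assumptions.

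**4. If an exact visit count were used as the attack count.** This is illustrative; the present form does not supply such a count. Let attacks be Poisson with mean m, each with probability q of one further visit. Mean visits are m(1 + q) and the variance is m(1 + 3q), so variance/mean is (1 + 3q)/(1 + q).

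| q (assumed) | Rate overstated by | Variance/mean (attacks: 1.00) |
|---|---|---|
| 0.1 | 10% | 1.3/1.1 = 1.18 |
| 0.2 | 20% | 1.6/1.2 = 1.33 |
| 0.4 | 40% | 2.2/1.4 = 1.57 |

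**5. Marker comparison.** Simulation under the same model: 50 v 50 children, equal true attack rates, 4,000 runs, p < 0.05. Rejection rates for mean attacks of 1, 2 and 3 a year:

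| q in the two groups | Mann-Whitney on visits | Fisher on any/none |
|---|---|---|
| 0.2 v 0.2 | 0.05, 0.05, 0.05 | 0.03, 0.03, 0.01 |
| 0.1 v 0.3 | 0.08, 0.15, 0.22 | 0.03, 0.03, 0.01 |
| 0.1 v 0.4 | 0.13, 0.26, 0.42 | 0.03, 0.03, 0.01 |

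Mann-Whitney on true attacks stays at about 0.05 throughout. Inflation appears only when q differs between groups and a count is analysed. The attack means, q and the even split are all assumed.

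**The case against.** The tempting stronger reading is that an attack seen by the GP and then in hospital is counted as two. The documents do not support it. The definition makes the attack the unit and the visit the condition for it to qualify, so on its wording an attack with two visits counts once. No text equates one visit with one attack. Nor does the form produce a two: both visits, if in the same month, share a band with a single visit. Only visits on either side of a form boundary are recorded twice.

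A reader might also infer that the attack rate will be inflated by tens of percent, or that the marker tests will give false positives. Those figures need visits to be substituted for attacks and, for the tests, repeat visits that differ by marker status. The plan states neither.

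Dates might come from the three-monthly reviews, from the medical notes, or from the case report form, which is not among the documents. Section 13.5 mentions access to notes under monitoring, audit and inspection, and nothing ties any of these sources to counting attacks. This lowers certainty about what could be salvaged. It does not supply a rule.

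Finally, this is a feasibility study, and an any/none analysis would be untouched. That stands, but section 11 does not commit to any/none, and any/none does not give the attack rate that a count-based trial would need.

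**Conclusion.** The concern holds as a gap in measurement and definition, not as a demonstrated bias. From the data the plan specifies, the number of attacks per child is undetermined, and no later analysis decision can recover it because the form carries neither dates nor an attack identifier. The size of the ambiguity follows from the form itself: four months in the lowest non-zero band fit 4 to 8 visits and, when those months are consecutive, as few as 2 attacks or as many as 8. The boundary-crossing shares rest on 30-day months and uniform timing. The rate, variance and false-positive figures show what could happen under assumed repeat-visit rates, not what is likely. With equal repeat-visit rates in the marker groups, the test keeps its level. The change is worth making because it concerns the primary outcome and must be in place before the data are collected.

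**What to change.** 1. In Question 3, ask for the date and place (GP, urgent care, hospital) of every unscheduled visit for wheeze in the month. First-visit dates alone would not be enough to apply a joining rule or vary it.
2. In section 6.1, state that visits within a prespecified interval of each other, including across two monthly forms, count as one attack. The study team should choose and justify the length, for example 7 days.
3. In section 11, state whether the primary variable is the number of attacks or any versus none, and name the test that goes with it.
4. Report total unscheduled visits as a separate outcome.

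The cost is one reworded online question, a sentence or two in each of sections 6.1 and 11, and slightly more work for parents in months with visits. The interval is partly arbitrary, so repeat the analysis with a second prespecified interval. With every visit dated, this needs no further data.
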